### **Study Drop Out:**

Subjects will be removed from the study if the Ob/Anesthesiologist determines there is a need to increase the concentration and volume of the local anesthetic solution.

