## **STUDY-WIDE NUMBER OF PARTICIPANTS:**

In a previous study in which 10 mL of a bupivacaine/fentanyl mixture was injected at 300 mL/h and 100 mL/hr, the duration to the first request for supplemental analgesia (manual bolus) was 356 minutes and 301 minutes with a 36% and 40% re-dose rate respectively.(7) We hypothesize that the group with low-volume bolus (6.25 mL) of greater density solution (0.1% bupivacaine with fentanyl 2.0 mcg/mL) will have fewer patients requiring supplemental analgesia than patients whose PIEB is delivered with a high-volume bolus (10 mL) of lower density local anesthetic (0.0625% bupivacaine with fentanyl 2.0 mcg/mL).

Assuming a 20% reduction in re-dose from 40% to 20%, a power of 0.8, and an alpha of 0.05, we estimate that we will need 91 patients per group. In order to account for drop-outs, we will recruit 110 patients per group.

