### **STUDY ENDPOINTS:**

**Primary outcome:** Need for supplemental physician-delivered bolus of local anesthetic.

**Secondary outcomes:** Time to first request for supplemental analgesia, total hourly bupivacaine consumption, mode of delivery, and motor block throughout labor and at 10 cm cervical dilation, sensory level throughout labor and at 10 cm cervical dilation, pain burden as defined as area under the pain-time curve, patient satisfaction.

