**Redoses:**

Up to three redoses of Bupivacaine .125% (10-15 mL) will be administered for inadequate pain control. The time to the first request for supplemental analgesia will be recorded on the study data sheet. The time, type and volume of bupivacaine used, and VAS scores before and 15 minutes after the re-doses will be recorded.

All other clinical management will be as per routine, and study participation will not interfere with anesthetic or obstetric care. Anesthesiologists will manage breakthrough pain in the usual manner (assessment of stage of labor and extend/density of neuraxial blockade, followed by the appropriate maneuver to reestablish adequate analgesia).

Following delivery, the patient will be asked to give one final VAS score and her overall satisfaction with labor using a 100 mm unmarked line (the left end labeled “not satisfied at all” and the right end labeled “extremely satisfied”). Mode of delivery, as well as the duration of the 1st and 2nd stage of labor, maximum oxytocin dose, maximum temperature recorded during labor, and any complaints for intrascapular pain will be recorded by study personnel.

Patient-Controlled Epidural Analgesia (PCEA) pump utilization data will be downloaded from epidural pumps after delivery. This will include the time to first PCEA request, the number of PCEA demands, the number of times that PCEA boluses were delivered, the total amount of local anesthetic consumed.

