**DATA AND SPECIMEN BANKING: NA**

**DATA AND SPECIMEN MANAGEMENT:**

Group sample sizes of 91 in group 1 and 91 in group 2 achieve 80.276% power to detect a difference between the group proportions of 0.1250. The proportion in group 1 (the treatment group) is assumed to be 0.1250 under the null hypothesis and 0.2500 under the alternative hypothesis. The proportion in group 2 (the control group) is 0.1250. The test statistic used is

the two-sided Fisher's Exact Test. The significance level of the test is targeted at 0.0500. In order to account for drop-outs, we will recruit 110 patients per group.

Categorical data between groups will be compared using a chi-square or Fisher's exact test, and continuous data will be compared using a two-tailed t-test or Mann Whitney U test as appropriate. Time outcomes will be compared between groups using a Kaplan-Meier survival analysis technique with log rank test. Patients undergo a cesarean delivery or who do not request supplemental analgesia will be censored at the time of delivery. Labor pain will be calculated using the area under the VAS-time curve using the trapezium rule.

The subjects' identity will be guarded by assigning a numerical code, which is only known by the principal investigator. Data are stored in a department computer which is password protected. Each study subject will be assigned a study code number. The code will be used to link study data to patient identification (name) in a separate database. Subject data will be stored on secured computers at Northwestern University. Data access will be password-protected and only available to study investigators. The data forms will be de-identified after the chart review prior to analysis. 5 years after manuscript publication, both electronic and paper data will be destroyed using the current departmental standards.

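### The Study Drop Out rule can take failures of the assigned regimen out of the primary comparison, and the plan does not say how these women are analysed

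*Combined protocol and SAP*

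**What the plan says.** Under the Study Drop Out section, a woman is "removed from the study if the Ob/Anesthesiologist determines there is a need to increase the concentration and volume of the local anesthetic solution". It asks for an increase in both concentration and volume, gives no time window, and does not say whether data already collected are kept.

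The primary outcome in Study Endpoints is "Need for supplemental physician-delivered bolus of local anesthetic". The Redoses section provides for such boluses within the study: "Up to three redoses of Bupivacaine .125% (10-15 mL) will be administered for inadequate pain control".

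Study-Wide Number of Participants and Data and Specimen Management both handle losses by over-recruitment: "In order to account for drop-outs, we will recruit 110 patients per group". Number of Local Participants repeats 91 needed and 110 recruited. The only censoring rule, in Data and Specimen Management, covers cesarean delivery and women who make no request. No section defines an intention-to-treat set, retains a woman who met the drop-out rule, or counts her as an event.

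**The concern.** The trial asks which combination of bolus volume and concentration better maintains analgesia. A clinician's decision that both must be increased is a judgment that the assigned regimen is not adequate. It is made after randomization and lies close to what the primary outcome measures. If such women leave the analysis, the remaining set describes re-dosing only among those whose regimen did not fail in this way. Over-recruitment restores the count but does not correct loss that depends on outcome.

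This is separate from the 90-minute exclusions under Exclusion criteria, because the drop-out rule can act at any point in labor.

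The boundary with the endpoint is also unclear. The re-dose solution (0.125%, 10–15 mL) is more concentrated than either maintenance solution (0.0625% and 0.1%) and at least as large as either programmed bolus (10 mL and 6.25 mL). The drop-out text refers to the local anesthetic solution without saying that it means the maintenance solution.

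**Working it through.** **The plan's own figure.** Study-Wide Number of Participants gives the inputs: "Assuming a 20% reduction in re-dose from 40% to 20%, a power of 0.8, and an alpha of 0.05". The two-sided normal-approximation sample size is 82 per group without continuity correction and 91 with it. Full enumeration of the "two-sided Fisher's Exact Test" at 91 per group gives 80.8% power, so 91 reproduces. (Data and Specimen Management rests its power statement on another pair of rates, 0.125 and 0.25. That conflict is a separate matter, and I do not use that pair here.)

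**Drop-out allowance.** 110 − 91 = 19 women per arm, and 19/110 = 17.3%, for all causes.

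**Effect of removal.** Let p be the true re-dose rate in an arm and f the fraction of its failures removed under the drop-out rule. I assume that every removed woman is one who would count as a failure.

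- Observed rate = p(1 − f)/(1 − pf)
- Women left = n(1 − pf)

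Examples:

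- p = 0.40, f = 0.25: 0.30/0.90 = 33.3%
- p = 0.20, f = 0.25: 0.15/0.95 = 15.8%
- p = 0.40, f = 0.50: 0.20/0.80 = 25.0%
- p = 0.20, f = 0.50: 0.10/0.90 = 11.1%
- p = 0.20, f = 0.10: 0.18/0.98 = 18.4%

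The documents give no value for f, so the table shows a range. The starting size also matters. Starting from 91 assumes that all 19 spare women are already lost to other causes. Starting from 110 assumes no other losses. Power is by exact enumeration of the two-sided Fisher test at 0.05, with the women left rounded to whole numbers.

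| Failures removed (40% arm / 20% arm) | Observed rates | Difference, points | Power from 91 | Power from 110 |
|---|---|---|---|---|
| none | 40.0% / 20.0% | 20.0 | 81% | 88% |
| 25% / 25% | 33.3% / 15.8% | 17.5 | 73% | 82% |
| 50% / 50% | 25.0% / 11.1% | 13.9 | 58% | 68% |
| 25% / 10% | 33.3% / 18.4% | 15.0 | 57% | 67% |
| 50% / 25% | 25.0% / 15.8% | 9.2 | 27% | 31% |
| 0% / 25% | 40.0% / 15.8% | 24.2 | 95% | 98% |

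The last row shows that the difference can also be enlarged.

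**No true difference.** With 40% in both arms and 25% of failures removed in one arm only, the observed rates are 33.3% and 40.0%. Starting from 110 per arm, the chance of a significant result is about 16%, against a nominal 5%.

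**How plausible are the fractions?** Removing half the failures in the 40% arm means 0.5 × 0.40 × 91 = 18 women, or 0.5 × 0.40 × 110 = 22. That is about equal to or above the 19 allowed for every cause, so the 50% rows are extreme. Removing a quarter means 9 to 11 women.

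**The case against.** Removal from the study is not the same as exclusion from the analysis. Up to three re-doses are given and recorded within the study, so a woman who had a re-dose before the drop-out decision already has her primary outcome on file. This is correct: exclusion is the likely reading, not a stated rule. But if retention is intended, no section says so, and the 91-to-110 allowance points the other way.

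A reader might infer that the low-concentration arm must lose more women because its solution is weaker. The documents do not support that. The rule requires more concentration and more volume, and the arms differ on these in opposite directions. The programmed bupivacaine dose is the same (10 mL × 0.625 mg/mL = 6.25 mL × 1 mg/mL = 6.25 mg), as is the patient-controlled dose (8 × 0.625 = 5 × 1 = 5 mg). Drugs or Devices also says the anesthesiologist is blinded. These features limit differential removal. They do not exclude it, since the plan's own hypothesis is that failure rates differ by arm.

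Nor does removal always weaken the contrast. With equal fractions removed, the odds ratio stays at 2.67 and the risk ratio rises from 2.00 to 2.11 (a quarter removed) or 2.25 (half removed). Only the two rates and the absolute difference fall.

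A reader might also infer that any re-dose triggers removal. That reading is strained, because the plan permits re-doses and makes them the endpoint. What stands is that the text does not draw the line.

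**Conclusion.** The concern holds as a gap in the analysis plan with a real risk of bias. A post-randomization rule closely tied to the primary outcome removes women at any time, and nothing in the plan keeps them in the primary comparison. The arm that loses the larger share of its failures looks better than it is, and the documents do not establish which arm that would be.

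The size depends on unknown removal fractions. If a quarter of failures are removed in both arms, power is 73–82%, so the recruitment margin may absorb the loss of power. If a quarter are removed in the 40% arm and a tenth in the other, it is 57–67%. The lowest figures, 27–31%, need half the failures removed in one arm and should be read as extreme, not expected. All these figures assume the plan's 40% versus 20%, that removed women would have counted as failures, and that they are excluded from the analysis.

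The point should be settled before analysis, because the plan as written permits the exclusion and the remedy is cheap.

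**What to change.** In the analysis text, state the following for every randomized woman who meets the drop-out criterion:

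- She is analysed in her assigned group. Data from before the decision are kept, and outcome collection continues (mode of delivery, motor block, satisfaction and the rest).
- The drop-out decision counts as a primary-outcome event. In the time-to-request analysis it is an event at the time of the decision, unless a request was already recorded earlier.
- The number of such women is reported by arm.
- A sensitivity analysis uses re-dose alone as the outcome.

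Separately, the sponsor must reconcile Study Drop Out with Redoses, so that the text distinguishes a re-dose given within the study from the drop-out trigger. Where that line lies is a clinical matter for the sponsor.

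The cost is protocol wording and continued collection of outcomes already planned; no patients or procedures are added. There is a small downside: the primary outcome becomes re-dose or drop-out decision, and secondary data collected after the decision partly reflect the changed solution.

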## **STUDY-WIDE NUMBER OF PARTICIPANTS:**

In a previous study in which 10 mL of a bupivacaine/fentanyl mixture was injected at 300 mL/h and 100 mL/hr, the duration to the first request for supplemental analgesia (manual bolus) was 356 minutes and 301 minutes with a 36% and 40% re-dose rate respectively.(7) We hypothesize that the group with low-volume bolus (6.25 mL) of greater density solution (0.1% bupivacaine with fentanyl 2.0 mcg/mL) will have fewer patients requiring supplemental analgesia than patients whose PIEB is delivered with a high-volume bolus (10 mL) of lower density local anesthetic (0.0625% bupivacaine with fentanyl 2.0 mcg/mL).

Assuming a 20% reduction in re-dose from 40% to 20%, a power of 0.8, and an alpha of 0.05, we estimate that we will need 91 patients per group. In order to account for drop-outs, we will recruit 110 patients per group.

## **STUDY-WIDE RECRUITMENT METHODS:**

Parturients who meet the inclusion criteria will be approached by one of the investigators, or one of the anesthesiology research nurses, for study participation on their arrival to the labor and

delivery unit. Parturients who are willing to participate in the study will provide written consent. Patient demographics will be collected at study enrollment.

## **MULTI-SITE RESEARCH: NA**

### **STUDY TIMELINES:**

The participants will be enrolled in the study at arrival, prior to request for labor analgesia. At the request for labor analgesia a vaginal exam will be performed by the obstetric or nursing team to ensure the patient still meets inclusion criterion. The patient will participate in the study from the time of initiation of combined-spinal epidural analgesia until the epidural catheter is discontinued after delivery. We estimate that it will take approximately 18 months to enroll 220 patients and perform data analysis.

### **STUDY ENDPOINTS:**

**Primary outcome:** Need for supplemental physician-delivered bolus of local anesthetic.

**Secondary outcomes:** Time to first request for supplemental analgesia, total hourly bupivacaine consumption, mode of delivery, and motor block throughout labor and at 10 cm cervical dilation, sensory level throughout labor and at 10 cm cervical dilation, pain burden as defined as area under the pain-time curve, patient satisfaction.

### **PROCEDURES INVOLVED:**

Parturients who meet the inclusion criteria will be approached by one of the investigators for study participation. Parturients who are willing to participate in the study will provide written consent. Patient demographics will be collected at study enrollment.

The research study team will determine group allocation by randomization via opaque sealed envelope. Participants will be randomized to one of two treatment groups based on a random computer-generated schedule (<https://www.randomizer.org>) and they will be blinded to the group to which they are assigned. The research study team will be blinded because the group will not be known other than group 1 or group 2 on the randomization card and on the pump. The CADD pump does not display the rate or the dose only group 1 or group 2.

Cervical dilation will be confirmed by a member of the obstetric team prior to initiation of CSE analgesia per routine practice. A baseline pain visual analog scale (VAS) score will be obtained using a 100-mm unmarked line with the end points labeled “no pain” and “worst pain imaginable.”

Labor analgesia will be initiated using CSE analgesia with 25 mcg of intrathecal fentanyl. An epidural test dose will be performed per routine (1.5% lidocaine with epinephrine 1:200, 3 mL).

Labor analgesia will be maintained using PIEB of local anesthetic with PCEA using the CADD-Solis pump (Smiths Medical). An unblinded anesthesia nurse will program the epidural pump and initiate the maintenance epidural infusion. The maintenance epidural solution for the high-

volume, low-concentration group will be bupivacaine 0.625 mg/mL with fentanyl 2.0 mcg/mL with a PIEB volume of 10 mL and patient-controlled epidural analgesia (PCEA) volume of 8 mL. The maintenance epidural solution for the low-volume, high-concentration group will be bupivacaine 1 mg/mL with fentanyl 2.0 mcg/mL with a PIEB volume of 6.25 mL and PCEA volume of 5 mL. The PIEB volume will be administered every 45 minutes. The first bolus will be given 30 minutes after intrathecal injection, as has been done in previous studies at our institution.(7) The bolus delivery speed will be 250 mL/h in both groups, which is our current practice. In addition to the programmed boluses patients will be able to administer PCEA boluses can be delivered every 10 minutes with a maximum of three PCEA boluses in a one-hour period. Fifteen minutes following the intrathecal dose, a VAS score and a sensory level of analgesia will be obtained. The following information will be obtained every two hours until complete cervical dilation (10 cm): VAS pain score, sensory level, a modified Bromage score (0 - no motor paralysis; 1 - inability to raise extended leg, but able to move knee and foot; 2 - inability to raise extended leg and to move knee, but able to move foot; 3 - inability to raise extended leg or to move knee and foot).

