## **INCLUSION AND EXCLUSION CRITERIA:**

### **Inclusion criteria:**

Age: 18 years and above, nulliparous parturients who present to the labor and delivery unit for an induction of labor or who are in spontaneous labor, and request neuraxial labor analgesia at  $\leq 5$  cm cervical dilation are eligible to participate.

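### The primary comparison ignores baseline pain and dilation; prespecified adjustment is an optional, low-cost precision gain, not the repair of an error

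*Combined protocol and SAP*

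**What the plan says.** STUDY ENDPOINTS defines the primary outcome as a yes/no event: "Need for supplemental physician-delivered bolus of local anesthetic". For its analysis, DATA AND SPECIMEN MANAGEMENT offers only a general rule: "Categorical data between groups will be compared using a chi-square" or Fisher's exact test. The power statement in that section names a two-sided Fisher test. No regression model, covariate, stratified test or stratified randomisation is mentioned.

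Three pre-treatment characteristics appear in the text, with different standing:

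- **Baseline pain.** PROCEDURES INVOLVED: "A baseline pain visual analog scale (VAS) score will be obtained", on a 100-mm line. This is a study measurement.
- **Cervical dilation.** The same section: "Cervical dilation will be confirmed by a member of the obstetric team prior to initiation of CSE analgesia", as part of routine care. STUDY TIMELINES gives the purpose of the examination at the analgesia request as an eligibility check. Neither place says that the value is entered as study data.
- **Type of labor.** Inclusion criteria: women "who present to the labor and delivery unit for an induction of labor or who are in spontaneous labor". This is eligibility wording; it is not listed as a data item.

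On size, STUDY-WIDE NUMBER OF PARTICIPANTS says: "Assuming a 20% reduction in re-dose from 40% to 20%, a power of 0.8, and an alpha of 0.05", and "we estimate that we will need 91 patients per group".

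**The concern.** The outcome counts any re-dose during labor, whatever the time at risk. In the earlier study cited in the sample-size section, first requests came at 301 and 356 minutes, so a woman with more labor ahead plausibly has more opportunity to need one. Dilation and induction status are pre-treatment proxies for that remaining time, and baseline pain may predict a re-dose in its own right. Duration of labor is recorded, but it arises after treatment starts and is not suitable for adjustment.

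If these variables are prognostic, an unadjusted comparison leaves some precision unused. It also leaves a visible chance imbalance with no planned response. For scale, assume half the women are induced. With simple randomisation at 91 per group, the SE of the difference in that proportion is √(0.5 × 0.5 × 2/91) = 0.074, so an imbalance of 10 points or more occurs in about 18% of trials. Adjustment fixed in advance is credible; adjustment added after seeing such an imbalance is much less so.

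**Working it through.** **Inputs from the documents:** 40% vs 20%, alpha 0.05, power 0.80, 91 per group (STUDY-WIDE NUMBER OF PARTICIPANTS); two-sided Fisher, or chi-square (DATA AND SPECIMEN MANAGEMENT). **Assumption:** the share of outcome variance explained by the baseline values, R². The documents give no figure, so it is varied.

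**1. Reproduce the plan's figure.** With mean rate 0.30:

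n = [1.960 √(2 × 0.30 × 0.70) + 0.842 √(0.40 × 0.60 + 0.20 × 0.80)]² / 0.20² = [1.2702 + 0.5323]² / 0.04 = 81.2, so 82 per group.

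With the continuity correction: (81.2/4) × [1 + √(1 + 4/(81.2 × 0.20))]² = 90.9, so 91 per group. The stated number reproduces.

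**2. Power of the planned test.** Exact enumeration at 91 per group, 40% vs 20%: 80.8% for two-sided Fisher, 84.7% for uncorrected chi-square.

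**3. Power with adjustment, by formula.** Multiply both variances by v = 1 − R²:

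power = Φ{[0.20 − 1.960 √(v × 0.42/91)] / √(v × 0.40/91)}

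| v | Variance change | Power |
|---|---|---|
| 1.02 | +2% (no prognostic value, cost of fitting) | Φ(0.979) = 83.6% |
| 1.00 | none | Φ(1.008) = 84.3% |
| 0.98 | −2% | Φ(1.039) = 85.1% |
| 0.95 | −5% | Φ(1.087) = 86.1% |
| 0.92 | −8% | Φ(1.137) = 87.2% |

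The gain at an 8% reduction is 87.2 − 84.3 = 2.9 points. In patients, an 8% reduction is worth about 0.08 × 182 ≈ 15 of the 182 analysed.

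**4. Check by simulation.** 2,000 trials per row, 91 per group, two baseline covariates; logistic regression with a standardised risk difference, compared with chi-square.

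| Approximate R² | Variance ratio, adjusted/unadjusted | Power, chi-square → adjusted |
|---|---|---|
| 0 | 1.01 | 84.2 → 84.3% |
| 0.01 | 0.99 | 85.4 → 86.5% |
| 0.04 | 0.95 | 83.3 → 85.0% |
| 0.06 | 0.95 | 85.8 → 88.0% |
| 0.09-0.12 | 0.90 | 83.3 → 87.8% |

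The Monte Carlo SE of each power is about 0.8 points (√(0.85 × 0.15/2000)). The last row supposes odds ratios of 2 and 1.5 per SD, which is stronger than the moderate range used for the conclusion.

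**5. Type I error.** In this simulation it was 5.3% adjusted vs 5.0% for chi-square. A separate run of 6,000 trials gave 5.5-5.8% adjusted vs 5.1-5.3% unadjusted. Part of the simulated power gain may therefore be a standard error that is slightly too small, which is why a small-sample correction belongs in the fix.

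**The case against.** The strongest reply is that nothing here is wrong. Randomisation makes the unadjusted test valid, and its type I error already allows for chance imbalance. It also reaches the target power under the 40% vs 20% assumption. All of this stands.

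Four stronger readings are tempting, and the documents support none of them:

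- **That the design has no power to spare.** This holds only for Fisher at 80.8%. The plan also allows chi-square, at 84.7%. Choosing it gains about 4 points with no covariates, more than adjustment is likely to add, and adjustment has to be judged against that same test.
- **That the precision is free.** The gain depends on a prognostic strength the documents do not give. The population is all nulliparous and dilation is capped at 5 cm, which may weaken the predictors. With none, adjustment costs a little.
- **That all the covariates are already collected.** This is stated only for baseline VAS. Dilation is examined but not said to be recorded, and induction status appears only in the eligibility text.
- **That adjustment would secure the trial's power.** The power statement in DATA AND SPECIMEN MANAGEMENT uses 12.5% vs 25%, in conflict with 40% vs 20%. At those rates and 91 per group, Fisher power is 51.5%. The normal approximation is 58% unadjusted and only 60% at R² = 0.05 or 68% at R² = 0.20. That conflict is a separate and weightier matter that must be reconciled in its own right; it neither supports nor refutes this point.

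One further objection also stands. A complete-case model that lost 4-8% of women to missing covariates would give back a gain of the same size, so adjustment is worthwhile only with a rule that keeps everyone in.

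**Conclusion.** The plan obtains at least one plausible baseline predictor and uses none in a valid, adequately powered (under 40% vs 20%) primary test. Prespecified adjustment is an optional improvement. Its expected size is a 0-8% lower variance of the risk difference and 0-3 points of power, for prognostic strength assumed between none and moderate. The downside is a loss of about 1-2% in precision if the covariates predict nothing, and possibly slight type I error inflation if no small-sample correction is used. The absence of any adjusted or stratified analysis is clear from the text; the size of the benefit is an assumption throughout.

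**What to change.** Before unblinding, amend DATA AND SPECIMEN MANAGEMENT to:

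1. Make the primary analysis a logistic regression of any physician-delivered bolus on arm and baseline VAS. Add dilation at the analgesia request and induced vs spontaneous labor once the plan states that both are recorded on the study data sheet.
2. Report a standardised (marginal) risk difference with a robust 95% CI and a small-sample correction to the standard error. This keeps the estimand of the unadjusted comparison; a conditional odds ratio would change it.
3. Handle missing covariates by a simple rule, such as mean imputation or a missing indicator, so that no woman is dropped.
4. Keep the unadjusted test as a sensitivity analysis, and say whether it is chi-square or Fisher.

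The cost is a few lines of plan and code, two routinely known items added to the data sheet, and a slightly less simple primary analysis. It needs no extra patients or procedures.
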